## 9.5. Routine Laboratory Data

Clinical chemistry, hematology and urinalysis laboratory measurements and value changes from baseline at each laboratory blood sample collection time point will be summarized. The count and percentage of patients who had normal or missing laboratory values at baseline and abnormal laboratory values post baseline will be presented. The lower limit of normal (LLN) and upper limit of normal (ULN) provided by the laboratories will be used as the criteria to determine abnormality. For each parameter, the denominator of the percentage will include patients with normal or missing assessments at baseline, and with at least one assessment post baseline. The numerator of the percentage will include patients who had at least one abnormal assessment post baseline among the patients that were counted in the denominator. Assessment collected at unscheduled visits or the Follow-up Visit will be included in the summary.

Shift of clinical laboratory results from baseline severity to the maximum post baseline severity will be presented for selected laboratory parameters. Clinical laboratory values will be also listed. Values outside the Laboratory's normal ranges and potentially clinically significant abnormal values will be flagged.

Estimated glomerular filtration rate (eGFR) will be calculated using the CKD-EPI cystatin equation ([Inker 2012](#)) and summarized as change from baseline, percentage change from

baseline, by categories (15 to <30, 30 to < 45, 45 to < 60, 60 to <90 and ≥90, as well as ≥10%, ≥25% and ≥= 50% decline from baseline) and by shift in categories.

Liver function test results will be summarized as change from baseline and as count and percentage of patients with normal baseline and abnormal post-baseline results in Alanine Aminotransferase (ALT), Aspartate Aminotransferase (AST), Alkaline Phosphatase (ALP) and bilirubin, with the following categories:

- ALT > 3xULN, > 5xULN, > 8xULN
- AST > 3xULN, > 5xULN, > 8xULN
- ALT and/or AST > 3xULN, > 5xULN, > 8xULN
- ALT and/or AST > 3xULN and total bilirubin > 2xULN and ALP < 2xULN
- ALT and/or AST > 3xULN and total bilirubin > 2xULN
- Bilirubin (total, indirect or direct) > 2xULN, >3xULN
- ALT or AST > 3 x ULN with symptoms including nausea, vomiting, anorexia, abdominal pain, fatigue, rash, dark-colored urine, light-colored bowel movements, jaundice, or fever

In addition, time to ALT, AST or bilirubin elevation since the first dose will be summarized by treatment groups.

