5.2. Exclusion Criteria

Patients will be excluded from the trial if any of the following criteria apply:

201. Other medically significant neurological conditions that could interfere with the assessment of ALS symptoms, signs or progression.
202. Presence at screening of any medically significant cardiac, pulmonary, gastrointestinal, musculoskeletal, or psychiatric illness that might interfere with the patient's ability to comply with study procedures or that might confound the interpretation of clinical safety or efficacy data, including, but not limited to:
 - a. Poorly controlled systemic hypertension
 - b. Clinically significant electrocardiogram (ECG) abnormalities that require medical attention (ie, persistent atrioventricular conduction block $>$ first degree, or acute myocardial ischemic changes)
 - c. New York Heart Association Class II or greater congestive heart failure
 - d. Chronic obstructive pulmonary disease
 - e. Gastrointestinal disorder that is likely to impair absorption of study drug from the gastrointestinal tract
 - f. $eGFR_{Cr}$ and $eGFR_{CysC} < 45.0$ mL/min/1.73 m² at screening
 - g. ALT or AST $\geq 3 \times$ ULN at screening
 - h. Urine protein creatinine ratio > 1 mg/mg (113 mg/mmol) at screening
 - i. Total bilirubin (TBL), direct or indirect bilirubin above the ULN.
 - j. History of Gilbert's Disease, Dubin-Johnson syndrome, or Rotor syndrome
 - k. Poorly controlled or brittle diabetes mellitus
 - l. Amputation of a limb
 - m. Cognitive impairment, related to ALS or otherwise that impairs the patient's ability to understand and/or comply with study procedures and provide informed consent
 - n. Cancer currently being treated (other than basal cell carcinoma, carcinoma in situ of the cervix, or squamous cell carcinoma of the skin excised with clean margins) or a history of cancer with an expected survival of less than 5 years. Breast cancer survivors with an expected survival of ≥ 5 years who are on long-term endocrine therapy are eligible.
 - o. Any other condition, impairment or social circumstance that, in the opinion of the Investigator, would render the patient not suitable to participate in the trial
 - p. Patient judged to be actively suicidal or a suicide risk by the Investigator
203. Known to have received reldesemtiv or tirasemtiv in any previous clinical trial

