7.3. Renal Function Monitoring and Study Drug Management

Study drug will be held if:

- $eGFR_{Cr}$ and $eGFR_{CysC} < 30.0$ ml/min/1.73m² or
- urine protein creatinine ratio (UPCR) is ≥ 3 mg protein/mg creatinine (or ≥ 339 mg protein/mmol creatinine)

Study drug may be restarted at half the dose, or 1 tablet twice a day (150 mg bid for those assigned to reldesemtiv) when:

- $eGFR_{Cr}$ and $eGFR_{CysC}$ is > 40.0 ml/min/1.73m² and
- UPCR is ≤ 1.5 mg protein/mg creatinine (or ≥ 170 mg protein/mmol creatinine)

Serum cystatin C, $eGFR_{CysC}$, serum creatinine, $eGFR_{Cr}$ and urine protein/creatinine ratio in a spot urine will be obtained and a microscopic urinalysis will be performed to look for cells and casts in accordance with the schedule of events; the medical monitors will be blinded to the UPCR (and the associated urinary creatinine and urinary protein), creatinine, serum cystatin C, $eGFR_{CysC}$, and $eGFR_{Cr}$ results. These renal related laboratory results will be reviewed by an unblinded physician who is not serving as the medical monitor for the trial. The unblinded physician will be unmasked to the renal lab results but will remain blinded to treatment assignments. The unblinded physician will contact the clinical trial investigator and medical monitors if laboratory results meet the criteria as described above that necessitate a study drug interruption. The Sponsor, all personnel charged with conduct of the trial outside of monitoring these laboratory data, and study sites will be blinded to the UPCR (and the associated urinary creatinine and urinary protein), creatinine, serum cystatin C, $eGFR_{CysC}$, $eGFR_{Cr}$ results.

Abnormal renal function tests meeting the above criteria will be repeated as directed by the unblinded physician, who will monitor repeat testing. The site investigator and medical monitors should discuss and agree that study drug can be resumed or alternatively permanently discontinued. Agreement by the patient, site investigator, and medical monitor must occur to determine that:

1. The study drug may be re-initiated at the lower dose of 150 mg bid (or placebo), or
2. The study drug should be permanently discontinued

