To accomplish this, the unblinded physician may direct the laboratory assessments (serum cystatin C, eGFR_{CysC}, serum creatinine eGFR_{Cr}, UPCR) to be repeated as often as 2-3 times weekly until a final disposition is reached (ie, re-initiation of study drug or placebo at 150 mg bid or permanent discontinuation) is reached.

Manifestations of renal toxicity, including clinically significant decreases in eGFR_{CysC} and eGFR_{Cr}, as well as increases of UPCR, as noted above, are considered adverse events of special interest and should be recorded on the appropriate CRF and reported to Cytokinetics Drug Safety within 24 hours of awareness.

Criteria for permanent discontinuation of study drug due to potential renal toxicity

Study drug **must** be discontinued permanently if the patient requires hemodialysis.

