### **9.2.4. Summaries of Adverse Events of Special Interest**

The following events are considered adverse events of special interest:

- Manifestations of renal impairment and toxicity defined in the protocol Section 7.3, including clinically significant decreases in eGFRCysC and increases of urine protein creatinine ratio
- Clinically significant elevated transaminases and/or bilirubin and manifestations of liver toxicity defined in the protocol Section 7.4 (eg, rash, abdominal pain, nausea and vomiting, fatigue, dark-colored urine, light-colored bowel movements, jaundice, loss of appetite, fever)

Adverse events of special interest recorded on the CRF will be summarized by SOC and PT. Patients with adverse events of special interest and their laboratory values will be listed.

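### The SAP's eGFR bands have no row below 15 and use cystatin C alone, so the banded and shift tables cannot place the lowest values or show who met the eGFR part of the protocol's hold rule

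*SAP*

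**What the plan says.** SAP 9.5 fixes the equation first: "Estimated glomerular filtration rate (eGFR) will be calculated using the CKD-EPI cystatin equation". The result is summarised as change and percentage change from baseline, then "by categories (15 to <30, 30 to < 45, 45 to < 60, 60 to <90 and ≥90", and the sentence goes on: "as well as ≥10%, ≥25% and ≥= 50% decline from baseline) and by shift in categories". The lowest absolute band therefore starts at 15. Three nested relative-decline categories sit beside the bands.

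Protocol 7.3 holds study drug when creatinine eGFR and cystatin C eGFR are below 30.0 ml/min/1.73m², or when the urine protein/creatinine ratio (UPCR) is 3 mg/mg or more. Study drug must be "discontinued permanently if the patient requires hemodialysis". The same section describes renal toxicity as an event of special interest, "including clinically significant decreases in eGFR_{CysC} and eGFR_{Cr}, as well as increases of UPCR".

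SAP 9.2.4 refers to protocol 7.3 for the renal events of special interest but words the content as "including clinically significant decreases in eGFR CysC and increases of urine protein creatinine ratio". Creatinine eGFR is not named there.

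**The concern.** Renal decline is an identified risk of this drug. In the Phase 2 trial, a fall in cystatin C eGFR was the commonest adverse-event reason for stopping study drug early (7/457, 1.5%; protocol 2.3.1), and protocol 7.3 provides for dialysis. A banded table of renal function should be open-ended at its severe end, and this one stops at 15.

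The second gap is a mismatch between rule and table. The protocol acts on two eGFR measures jointly, while the SAP bands only one. Protocol 2.3.1 also gives a reason not to set creatinine aside: the decline in cystatin C eGFR meant that the earlier creatinine rises could not be put down to transporter inhibition alone.

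At stake is how clearly the study report shows the most severe renal values and the number of patients who crossed the protocol's own renal threshold. No efficacy analysis is touched.

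**Working it through.** The plan gives no figure to reproduce on this point. Three checks apply.

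**1. Do the absolute bands cover every possible value?** The bands in SAP 9.5 are [15, 30), [30, 45), [45, 60), [60, 90) and 90 upward. Of the trial values 0, 5, 10, 14.9, 15, 29.9, 30, 44.9, 45, 60 and 90, those in no band are 0, 5, 10 and 14.9. The gap is every value below 15. The shift table built on these bands has the same gap.

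**2. Do the relative-decline categories catch these patients?** From baseline b, a value below 15 requires a decline of more than 100 × (1 − 15/b) per cent:

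- b = 90: 100 × (1 − 15/90) = 83.3%
- b = 60: 100 × (1 − 15/60) = 75.0%
- b = 45: 100 × (1 − 15/45) = 66.7%
- b = 30: 100 × (1 − 15/30) = 50.0%
- b = 25: 100 × (1 − 15/25) = 40.0%

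From any baseline of 30 or more, the patient is counted under at least 50% decline. Only a baseline cystatin C eGFR below 30 could lead to a value below 15 without meeting that category. Such a baseline could arise if the exclusion in protocol 5.2 is read as requiring both measures below 45, or if the value fell between screening and the last pre-dose sample.

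Being counted is not the same as being distinguished. A fall from 90 to 44 is 100 × (1 − 44/90) = 51.1%, and a fall from 90 to 10 is 100 × (1 − 10/90) = 88.9%. Both fall under at least 50%. The absolute bands would separate them, but they place only the first, in 30 to <45.

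**3. Can the tables show the eGFR part of the hold rule?** The rule needs both measures below 30. At any visit, the number with both below 30 cannot exceed the number with cystatin C eGFR below 30. That number is the 15 to <30 count plus the <15 count. The SAP tabulates the first term, omits the second, and gives no bands for creatinine eGFR. Neither the joint count nor its upper bound can be read from the tables.

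The liver categories in the same SAP section give a useful comparison. They are open-ended at the severe end (ALT or AST >3×, >5× and >8× ULN; bilirubin >2× and >3× ULN), use cut-offs that appear in protocol 7.4, and include rows that combine transaminases with bilirubin. The renal categories have neither an open severe end nor a joint row.

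**The case against.** The strongest reply is that nothing serious would be hidden. The at least 50% decline category counts nearly every such patient, and the change and percentage-change summaries use every value. SAP 9.5 lists all laboratory values with flags. SAP 9.2.4 summarises events of special interest and lists those patients with their laboratory values. A dialysis case would also be expected among the serious events and discontinuations. All of this stands. A reader who stops at the list of bands might infer that the worst renal outcomes fall in no category at all; the rest of the same sentence in the SAP shows otherwise.

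A reader might likewise infer that creatinine eGFR goes unreported. It does not: protocol Table 9 lists it as a chemistry parameter, so the general chemistry summaries and listings should include it. SAP 9.2.4 cites protocol 7.3 and summarises what is recorded on the CRF, so a creatinine-based event recorded there would be included. The mismatch in that section is one of wording. Banding on cystatin C is also defensible as a main presentation, because the drug was already known to raise creatinine.

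The table shells are in a separate document and may already contain a <15 row. That is possible, but it would not correct the SAP text.

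Two further replies carry less weight. Adverse-event reporting is an imperfect substitute, because sites, sponsor and medical monitors are blinded to these renal results and depend on the unblinded physician to report threshold breaches (protocol 7.3). Down-titration alone does not identify who met the rule, because some placebo patients receive dummy down-titrations (protocol 6.3) and other adverse events can also lead to a reduction (protocol 6.6). Interruption reasons are recorded, but SAP 9.5 plans no count against the laboratory criterion.

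**Conclusion.** The point holds as a limited reporting gap. Every eGFR below 15 lacks an absolute band and a shift cell. The banded and shift tables use cystatin C eGFR alone and so cannot show who met the eGFR part of the hold rule. SAP 9.2.4 is narrower in wording than protocol 7.3.

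The documents do not support the stronger reading that severe cases vanish from the report. Such a patient would normally be counted under at least 50% decline and would appear in the change summaries and listings, but could not be told apart in that category from less severe declines of 50% or more.

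The number affected cannot be derived from the documents. It is probably small: Phase 2 had 7/457 stopping for a fall in cystatin C eGFR, mean eGFR was essentially stable by two weeks, and nobody required dialysis. The conclusion assumes that the tables are produced as SAP 9.5 describes them.

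**What to change.** In SAP 9.5:

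- Add a <15 band to the category table and to the shift table, so that every value has a row.
- Repeat the bands and the shift for creatinine eGFR.
- Add a count, by treatment group, of patients with both eGFR measures <30 at the same assessment. Count UPCR ≥3 mg/mg beside it, because that is the other part of the protocol 7.3 rule and the eGFR count alone would miss patients held on UPCR.

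In SAP 9.2.4, reconcile the description of renal events of special interest with protocol 7.3, which names both eGFR measures.

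The cost is one extra band, one repeated set of tables, one short count and a wording change, all from data already collected. No clinical threshold changes. Making the change before database lock avoids deciding how to display the lowest values after unblinding.

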Clinically significant elevated transaminases and/or bilirubin and manifestations of liver toxicity (eg, rash, abdominal pain, nausea and vomiting, fatigue, dark-colored urine, light-colored bowel movements, jaundice, loss of appetite, fever), including elevations that prompt study drug discontinuation, are considered adverse events of special interest and must be recorded on the appropriate CRF and reported to Cytokinetics Drug Safety within 24 hours of awareness.

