## **6.6. Baseline Definition**

Unless otherwise specified, baseline is defined as the last available measurement taken prior to administration of the first dose of study drug.

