## 9.6. Vital Signs

Blood pressure, heart rate, respiratory rate, body weight and oral temperature will be collected at the time points specified in the protocol. For each assessment time point, absolute values and changes from baseline of the vital signs will be summarized.

The count and percentage of patients who had normal or missing values at baseline and Potentially Clinically Significant (PCS) values post baseline will be presented. The PCS criteria are specified in [Table 7](#). For each parameter, the denominator of the percentage will include patients with non-PCS or missing assessments at baseline, and with at least one assessment post baseline. The numerator of the percentage will include patients who had at least one PCS assessment post baseline among the patients that were counted in the denominator. Assessment collected during unscheduled visits or the Follow-up Visit will be included in the summary.

All collected vital signs and assessment time will be listed, and values outside the normal ranges will be flagged.

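### SAP 9.5 ties the ALT/AST >3×, >5×, >8×ULN and symptomatic >3×ULN counts to a normal baseline, and the available SAP text commits to no all-patient count by threshold and arm

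*SAP*

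**What the plan says.** SAP 9.5 first describes a general laboratory abnormality table. For it, the lower limit and the "upper limit of normal (ULN) provided by the laboratories will be used as the criteria to determine abnormality", and the denominator is patients with a normal or missing baseline and at least one later value.

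The liver paragraph follows. It plans change from baseline, and results "as count and percentage of patients with normal baseline and abnormal post-baseline results in Alanine Aminotransferase (ALT", with AST, alkaline phosphatase and bilirubin named next. Listed beneath are ALT, AST, and ALT and/or AST at >3×, >5× and >8×ULN, two combined ALT/AST-plus-bilirubin rows, a bilirubin row and a row for ALT or AST >3×ULN with symptoms. No denominator is given for these rows.

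Four other outputs touch the same patients:
- SAP 9.5, shift table: "Shift of clinical laboratory results from baseline severity to the maximum post baseline severity will be presented for selected laboratory parameters".
- SAP 9.5, timing: "time to ALT, AST or bilirubin elevation since the first dose will be summarized by treatment groups".
- SAP 9.5, listings: all laboratory values, with out-of-range values flagged.
- SAP 9.2.4: "Adverse events of special interest recorded on the CRF will be summarized by SOC and PT", with affected patients' laboratory values listed. Protocol 7.4 places "Clinically significant elevated transaminases and/or bilirubin and manifestations of liver toxicity" in this class.

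On entry, Protocol 5.2 (item 202g) excludes ALT or AST of 3×ULN or more at screening. Protocol 5.1 (item 110) accepts other out-of-range results that the investigator judges not clinically significant. Under SAP 6.6, "baseline is defined as the last available measurement taken prior to administration of the first dose of study drug" unless otherwise specified.

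**The concern.** Hepatic injury is one of the two organ risks for which Protocol 2.3.1.1 sets a mitigation strategy, and the rows in SAP 9.5 are the only summary by ULN threshold that the SAP text describes. A patient who starts above ULN needs the smallest rise to cross 3×ULN, yet is the one left out. The SAP treats the other organ risk differently: in the same section, eGFR is summarised by category, by percentage decline and by shift, with no normal-baseline condition.

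The rows are also narrower than the rules that take patients off drug. What is at stake is a complete count of threshold crossings in the study report, and a figure that can be set beside the Phase 2 result.

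**Working it through.** The plan states no figure for this point, so the check sets the texts side by side and then sizes the gap under stated assumptions.

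**1. Who can enter but not be counted.** Entry allows ALT/AST above 1×ULN and below 3×ULN, subject to the investigator's judgement. The rows require a normal baseline, and SAP 9.5 judges abnormality by the laboratory range. The patients between are randomised but not counted. Safety laboratory tests are also drawn on Day 1 (Protocol 1.3). If that sample precedes dosing, it sets the baseline, so a patient normal at screening and above ULN on Day 1 also drops out.

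**2. Rows against stopping rules (Protocol 7.4).**

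| Criterion | Baseline in Protocol 7.4 | Baseline in SAP 9.5 |
|---|---|---|
| ALT or AST >8×ULN | any | normal |
| >5× to <8×ULN for at least 2 weeks | any | normal (row is >5×ULN) |
| >3×ULN with hepatitis signs or symptoms | any | normal |
| >3×ULN with bilirubin >2×ULN (or INR >1.5) | below ULN | normal |

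A patient starting at 1.5×ULN who reaches 9×ULN (a 6-fold rise) must stop drug permanently but does not appear in the >8×ULN row. The fourth line agrees; the first three do not.

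**3. Rise needed to reach 3×ULN from b×ULN = 3/b.** b = 1: 3.0-fold. b = 1.5: 2.0. b = 2: 1.5. b = 2.5: 1.2.

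**4. The Phase 2 figure.** Protocol 2.3.1 reports ALT or AST >3×ULN in 24 (7.0%) reldesemtiv and 1 (0.9%) placebo patients. 24/343 = 7.0% and 1/114 = 0.9%, and 343 + 114 = 457, the participant total in that section. The denominators are inferred, but they point to all-patient incidence.

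**5. Size under assumptions.** Planned arms: 555 × 2/3 = 370 and 555/3 = 185. Let f be the share with raised baseline ALT/AST and R their risk of crossing a threshold relative to the others. Neither is in the documents. Patients outside the rows = 370f and 185f. Share of cases outside = fR / ((1 − f) + fR). For scale, if 7.0% of 370 reldesemtiv patients exceed 3×ULN, there are 25.9 cases in all.

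| f | Patients outside (reldesemtiv, placebo) | R = 1 | R = 2 | R = 4 |
|---|---|---|---|---|
| 5% | 18.5, 9.25 | 5.0% (1.3 cases) | 9.5% (2.5) | 17.4% (4.5) |
| 10% | 37, 18.5 | 10.0% (2.6) | 18.2% (4.7) | 30.8% (8.0) |
| 20% | 74, 37 | 20.0% (5.2) | 33.3% (8.6) | 50.0% (13.0) |

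**6. Effect on the comparison.** If the denominator is restricted as well, the displayed rate is the all-patient rate divided by (1 − f) + fR. With f = 20% and R = 4 the divisor is 1.6, so 7.0% would show as 4.4% and 0.9% as 0.6%. The ratio between arms is unchanged when f and R are the same in both.

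**The case against.** **Normal might mean not meeting the category.** SAP 9.6 speaks of normal or missing baseline values and then says "the denominator of the percentage will include patients with non-PCS or missing assessments at baseline"; SAP 9.7 does the same for ECG. Carried over, nearly everyone would qualify, since 3×ULN or more is excluded at screening. This reading is possible but not the natural one. Those sections restate the denominator in terms of the tabulated criterion; SAP 9.5 does not, and its only definition of abnormal is the laboratory range. A programmer following the text would drop these patients.

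**The combined rows follow the protocol.** This stands. The combined stopping criterion in Protocol 7.4 specifies a baseline below ULN, so a normal-baseline view of those rows matches it. A reader might infer that the plan departs from the protocol on its most serious hepatic signal; the text does not support that.

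**The cases are not lost.** This also stands. Special-interest reporting has no baseline condition, and the listings show every value. A reader might infer that hepatic cases would be hidden, but individual threshold, symptomatic or combined cases should be identifiable. What is missing is a committed incidence row.

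**The shells may settle it.** SAP 6.4 treats the shells as part of the SAP, and SAP 12.2 places the display specifications in a separate document that was not available. They could name the shift parameters, severity bands and denominators. But SAP 6.4 also says that differences in analysis methods or data handling need documentation, so the population rule belongs in the text.

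**It is a display preference.** A normal-baseline view is a fair measure of treatment-emergent change, and a small rise from a raised baseline is less specific. That is a reason to keep it, not to make it the only threshold view.

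**Conclusion.** The point holds for the single-analyte ALT/AST rows and the symptomatic >3×ULN row. As written, these count only patients whose baseline is within the laboratory ULN, while entry and the corresponding stopping rules do not require that. Nothing else in the available SAP text commits to all-patient incidence by ULN threshold and arm: the shift parameters and severity scale are unnamed, and time to elevation has no threshold. For the combined rows an all-patient count would be a supplement, not a correction. The bilirubin-only row is hardly affected, because raised bilirubin is excluded at entry.

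The number of cases is unknown; the range in the working follows entirely from the assumed f and R. The conclusion rests on the natural reading of normal baseline and on the SAP text without its shells.

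A reader might infer a biased safety comparison. The documents do not support that: the condition uses a pre-dose value and applies alike to both arms. If relative risk in raised-baseline patients differed by arm, that would be a subgroup difference which the table fails to show, not bias in what it does show. No efficacy result or stopping rule changes. This is a modest gap in safety reporting that should be closed before database lock.

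**What to change.** In SAP 9.5:
- Tabulate each ALT/AST threshold row and the symptomatic row for all Safety Analysis Set patients with at least one post-baseline value, by arm and study period, split by baseline ALT/AST ≤ULN and >ULN. Keep the normal-baseline view as one column.
- Add the same split for the combined rows as a supplement, and state which analytes must be normal at baseline for them.
- Say how patients with a missing baseline are handled, since the general table includes them and the liver sentence is silent.
- Name ALT and AST among the shift-table parameters and set the bands, for example ≤1×, >1 to 3×, >3 to 5×, >5 to 8× and >8×ULN.

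The cost is a few sentences and one extra breakdown, with no new data. Reported hepatic counts may be slightly higher.
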